#### 1. INTRODUCTION

Gingivitis is an oral disease condition affecting 50% to 90% of adults globally (Albandar and Rams, 2002). Not only is it common in the adult population, but it is a precursor to periodontal disease, which is a more severe condition of gum disease that permanently damages the soft tissues and the bone supporting the teeth (Löe et al., 2009). It is an issue that the investigators do not want to overlook since it has also been proven that periodontitis exacerbates different systemic diseases, such as diabetes and atherosclerotic vascular disease (Lockhart et al., 2012; Mealy et al. 2006). Previous studies and clinical research have shown that combining antimicrobial treatment with non-surgical periodontal therapy, such as scaling and root planning, is an efficient way to tackle periodontal disease (Kapoor et al. 2012). However, modern practitioners are looking for an alternative therapy, as antibiotics are innocuous drugs by nature and can lead to several side effects, damage to our commensal bacterial flora and favour the development of antibiotic-resistant bacteria (De Nies et al. 2023; Soares et al. 2012). Knowing the complexities associated with the treatment and management of periodontal disease, the primary strategy for success lies in its prevention. Therefore, it is also imperative to identify effective methods for treating and preventing gingivitis.

The gingivitis pathology can be reversed by reduction or removal of microbial plaque that accumulates on hard and soft tissues and is considered standard of care in the industry (Berezow Alex and Darveau Richard, 2010, van der Weijden and Slot, 2011). Regular oral hygiene in combination with therapeutics that delivers an anti-microbial benefit is thought to mitigate the onset of gingivitis (van der Weijden and Slot, 2011, Gunsolley, 2006). However, testing therapeutics for prophylaxis benefit to mitigate development of gingivitis has not been fully examined.

The classical model of experimental gingivitis (EG) was developed in 1965 by Loe and Silness who convincingly demonstrated the causative relationship between the accumulation of dental plaque and the development of clinically evident gingivitis in healthy young adults abstaining from all oral hygiene practices for a 21-day period. Furthermore, on resuming customary oral hygiene practices, all study participants demonstrated a return to gingival health within two weeks (Loe et al., 1965). To understand how the participants of this study returned so quickly to gingival health we can reflect on our current understanding that our clinically healthy state is an active and dynamic process.

Neutrophils, a type of white blood cell (leukocyte), represent a key component of the innate defence system that protects periodontal tissue from both gingivitis and periodontitis. Not only are they the first line of cellular defence, but they are among the most abundant leukocytes within the periodontal tissues (Hirschfeld, 2020). For example, gingivitis is associated with a significant increase in the number of neutrophils that migrate to periodontal tissue. In contrast, individuals with too few neutrophils brought about by either congenital deficiencies in neutrophil numbers, or transit (LAD 1 and 2) or have an induced neutropenia by chemical induction with antimitotic agents such as cyclophosamide invariably develop periodontitis. Likewise, studies in KO mice that are defective in neutrophil transit also develop periodontitis. Consistent with the key contribution of neutrophils to both gingivitis and periodontitis, neutrophil transit to gingival tissue is highly regulated. The periodontium contains a highly orchestrated expression of select innate host defense

mediators that facilitate the transit of neutrophils from the highly vascularized gingival tissue to the gingival crevice, where they form a "wall" between the host tissue and the dental plaque biofilm.

However, the prolonged presence of neutrophils in gingival tissue is not tolerated in the healthy state. For example, the failure to down regulate orchestrated neutrophil transit. Oresults in an increase in neutrophil numbers in gingival tissue and a significant increase in per iodontal bone loss. Therefore, neutrophil homing to the gingival crevice is highly regulated such that under conditions of periodontal health the appropriate amount of neutrophils are present to maintain control of dental plaque bacterial growth and yet not elicit tissue damage. Evaluation of oral and blood neutrophils during experimental gingivitis showed that people with uniquely high inflammatory response had an exaggerated polymorphonuclear neutrophil response both in the oral cavity as well as in the blood (Wellappuli 2017).

Gingivitis is a reversible inflammatory condition caused by the accumulation of dental plaque and the associated disruption of the host–microbial homeostasis. During gingivitis, the microbial community transitions from being dominated by gram-positive health-associated bacteria, such as Streptococcus species, to gram-negative periopathogens, including species of the genera Porphyromonas, Tannerella, Treponema and Prevotella. This dysbiotic shift triggers inflammatory responses, leading to tissue damage and, in some cases, progression to periodontitis. Those pathogenic bacteria also contribute to the production of volatile sulfur compounds; as a result, people with gingivitis have an increased probability of having halitosis by 3.6 times (Lee et al. 2023).

A recent study (Kerns, 2023) on human experimental gingivitis identified three distinct host response phenotypes—high, low, and slow responders—based on clinical, inflammatory, and microbial parameters:

- 1. High Responders: Rapid plaque accumulation accompanied by a significant increase in gramnegative periopathogens and elevated inflammatory markers, such as interleukin-1β (IL-1β).
- 2. Low Responders: Similar plaque accumulation to high responders but lower inflammation, suggesting a more muted host response to bacterial dysbiosis.
- 3. Slow Responders: Delayed plaque accumulation and microbial succession, with prolonged dominance of health-associated Streptococcus species. This group exhibited delayed or reduced inflammation, demonstrating a more resilient microbial community and host response.

The microbial analysis revealed that the persistence of beneficial Streptococcus species, such as S. sanguinis and S. oralis, in slow and low responders correlates with a protective effect against the emergence of periopathogens and the associated inflammatory cascade. Conversely, the loss of these beneficial bacteria in high responders was linked to more severe inflammation, highlighting the critical role of the oral microbiome in modulating gingivitis severity.

Lantibiotic salivaricins are polycyclic peptides containing lanthionine and/or  $\beta$ -methyllanthionine residues that are produced by certain strains of Streptococcus salivarius, which almost exclusively reside in the human oral cavity. These molecules importance stems from their antimicrobial activity towards relevant oral pathogens which has been applied through the development of salivaricin-producing probiotic strains. However, salivaricins may also prove

to be of great value in the development of new and novel antibacterial therapies in this era of emerging antibiotic resistance (Barbour, Wescombe, & Smith, 2020). In a study by Barbour & Philip 2014, they found that the bacteriocin, levan-sucrase production and basic safety features of S. salivarius strains isolated from healthy Malaysian study participants demonstrating their potential for use as probiotics. A new bacteriocin production medium was developed with potential scale up application for pharmaceuticals and probiotics from S. salivarius generating different lantibiotics. This is relevant for the clinical management of oral cavity and upper respiratory tract in the human population. Appendix 1 includes a summary table that lists the relevant clinical trials that utilized S. salivarius.

Proposed Solution: S. salivarius SALI-10 to be used as a probiotic to help prevent gingivitis

We propose using a novel strain, Streptococcus salivarius SALI-10, as a targeted microbial intervention to modulate the oral microbiome and prevent gingivitis. S. salivarius SALI-10 is hypothezised to:

- Maintain a stable population of beneficial streptococci during plaque accumulation.
- Inhibit the growth of periopathogens such as Porphyromonas, Tannerella and Prevotella through competition and production of Salivaricin 10.
- Delay or suppress the dysbiotic shift to gram-negative dominance, thereby reducing the inflammatory response.

By preserving microbial homeostasis, SALI-10 may emulate the microbial resilience observed in slow responders, offering a novel strategy for gingivitis prevention.

#### 2. STUDY OJECTIVES

- 1) The aim of this study is to evaluate the efficacy of S. salivarius SALI-10 in modulating the oral microbiome and preventing gingivitis, using a placebo-controlled experimental gingivitis model. Specifically, the investigators aim to:

  Microbiome Modulation:
  - Assess the ability of SALI-10 to maintain higher levels of beneficial streptococci (S. sanguinis, S. oralis, S. parasanguinis and SALI-10) during plaque accumulation.
  - Determine whether SALI-10 prevents or delays the increase of gram-negative periopathogens (Tannerella, Prevotella, and Porphyromonas) and dysbiosis.
- 2) To evalute the effects of probiotic Sali-10 intake regarding clinical parameters of periodontal health during an experimental gingivitis.
- 3) To assess differences in the onset of gingivitis, the extent of the condition, and its resolution among experimental and control groups.
- 4) To evaluate the capability to establish or increase oral colonization by *Streptococcus* salivarius SALI-10. The expected outcomes will be attributed to the effect of antimicrobial and immunomodulation metabolites (mainly, the natural product Salivaricin 10) produced by this strain present in the probiotic.
- 5) To analyze the level of sulfured compounds emitted from the oral cavity with a halimeter (Halimeter PLUS) from each study participant to assess the level of halitosis objectively, then evaluate the difference between the control and test groups as they go through the experimental gingivitis clinical trial.

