#### 3. STUDY OVERVIEW

This research study is designed to evaluate a new strain of *Streptococcus salivarius* containing probiotic properties for its effect on gingivitis including the oral neutrophil phenotype and oral microbiome modulation during an induced gingivitis state. A 7-week (8 appointments, 7 weeks) clinical study will be conducted to evaluate a probiotic for therapeutic effects that aim to delay the onset of experimental gingivitis and hasten the resolution of the disease.

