#### 4.2 Study Population

Advertisements (Appendix 2) will be placed at University of Toronto downtown campus to invite volunteers who are interested to participate. All study participants will undergo informed consent process, prior to enrollment in the study. Categorization of participants and sites will be based on the clinical assessments. Other than the study-related oral health history recorded, there is no intention to obtain information from the participants" other dental or medical records. Sixty (60) qualifying volunteers that agree to participate and sign all corresponding forms will be enrolled.

The first participant will be assigned a number, and all the following enrolled participants will be assigned consecutive numbers by accession. The following inclusion and exclusion criteria will be utilized in this study.

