#### 4.3 Inclusion Criteria:

- 1) Male or female volunteers aged 18-70 years
- 2) In good general health, ASA I
- 3) No clinical signs of gingival inflammation at >90% of sites observed
- 4) Absence of Periodontal Pockets, Probing Depth (PD) < 3.0 mm on all teeth/site
- 5) Absence of Clinical Attachment Loss (CAL) = 0 mm
- 6) No periodontal disease history
- 7) Have at least 20 gradeable teeth
- 8) Non-smokers
- 9) Fluent in English
- 10) For study participants of childbearing potential, both men and women, at least one of the following birth control measures must be used: abstinence, hormonal birth control (oral, injectable, transdermal, intra-vaginal), intrauterine devices, confirmed successful vasectomy, or condoms.

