# 6. STUDY PROCEDURES

# 6.1 Randomized Assignment and Product Blinding

Qualified study participants will be randomly assigned to one of two study groups, either Group A or Group B, using randomization software. To maintain blinding, the manufacturer will produce both probiotics and placebo lozenges, dispense them in identical, opaque bottles, and label them as either Group A or Group B. The assignment of probiotics to one of these groups will be determined by the manufacturer and disclosed only at the study's conclusion. Each bottle will be labeled with a code (either letter A or B, followed by a number) and emergency contact information. The products will be distributed in sealed boxes that look identical to prevent any differences in appearance or packaging between study groups. Each product inside the box will be overwrapped and include instructions for at-home use and safety information, including emergency contact details.

To monitor study participant compliance, the investigators will use a pharmaceutical scale to ensure the number of lozenges remaining in the bottle matches the expected count at each study visit. A scale will be used to avoid the operator from seeing the lozenges, in order to preserve blindness in this study (placebo and probiotic lozenges are not perfectly identical).

Study participants will be assigned a unique identification number in chronological order (e.g., from 1 to 60) as they enroll in the study. These identification numbers have been pre-assigned to a study group based on a computer-generated randomization list provided by an independent statistician. Cohabitant study participants will be assigned to the same study group and receive the same products. Study participants will be instructed to avoid using any other oral hygiene products. There will be no dietary restrictions during the study.

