# 8.0 STATISICAL ANALYSES

Correlations between tissue and blood neutrophil subsets and standard periodontal disease parameters from oral exam will be assessed. Data will be complied in SPSS version 20. Changes in the clinical parameters of experimental gingivitis such as bleeding on probing, gingival index, plaque index and probing depths during day 0, 7, 14, 21, 28 and 35 will be compared using one-way analysis of variance (ANOVA) followed by Tukey multiple comparison.

Oral neutrophil counts as well as neutrophil subset formation during day 0, 7, 14, 21, 28 and 35 in oral rinse samples as well as blood samples will be compared using one-way analysis of variance (ANOVA) followed by Tukey multiple comparison.

Multiple sites within each study participant will be evaluated using a Gingival Bleeding Index (BOP) at baseline and 3-week post product use exams. The gingivitis bleeding scores will be averaged to provide a mean score per study participant for each exam period. Product means and standard deviations will be calculated for each time period. Analysis of Variance techniques (possibly including Analysis of Covariance using the baseline scores as the covariant) will be used to compare the difference between the two test treatments using the 95% confidence level ( $p \le 0.05$ ). The correlation of baseline to post-treatment results will be assessed graphically. If there is evidence of correlation, the baseline result will be included in the ANOVA model to adjust for baseline differences.

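### Delayed onset of gingivitis is an objective and an overview aim, but the clinical analyses fixed in Section 8.0 do not address it, and a single late mean cannot separate later onset from milder disease

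*Protocol*

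**What the plan says.** Section 2, objective 3: "To assess differences in the onset of gingivitis, the extent of the condition, and its resolution among experimental and control groups". Onset, extent and resolution are listed as three separate things. Section 3 describes effects that "aim to delay the onset of experimental gingivitis and hasten the resolution of the disease". The first-listed objective is to "evaluate the efficacy of S. salivarius SALI-10 in modulating the oral microbiome and preventing gingivitis". No objective is called primary.

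Section 8.0 fixes two clinical analyses:

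- BOP, GI, plaque index and probing depth over Days 0, 7, 14, 21, 28 and 35 "will be compared using one-way analysis of variance (ANOVA) followed by Tukey multiple comparison".
- BOP averaged per participant, compared between the two products by ANOVA or ANCOVA, at baseline and at one exam three weeks after product use.

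Sections 6.5 to 6.7 record GI and BOP for each participant at every weekly visit. No section states when a participant counts as having developed gingivitis. The nearest rule is inclusion criterion 3: "No clinical signs of gingival inflammation at >90% of sites observed".

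**The concern.** A lower mean score at one visit can arise because disease started later and then progressed at the usual speed, or because it started on time and progressed more slowly. The protocol itself treats these as different. Its Introduction separates low responders (similar plaque, less inflammation) from slow responders (delayed plaque and microbial succession), and proposes that SALI-10 may mimic the slow ones.

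If Section 8.0 is run as written, a positive result supports a lower mean score. A statement that onset was delayed would go beyond the analysis.

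**Working it through.** **Step 1. Objective against analysis.** The plan gives no figure for onset to reproduce, so the texts are compared first.

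- A one-way ANOVA has one factor. If the factor is day, the arms are not compared. If it is arm, each day is tested separately and there is no arm-by-visit comparison. Tukey's procedure adds nothing with two groups, so day (six levels) is the more natural reading.
- The BOP comparison names both products but uses one follow-up exam. Product starts at Day -14 (Section 6.5.1), so three weeks could mean Day 7 (after first use) or Day 21 (end of induction).

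**Step 2. One visit.** Illustrative model; every input is an assumption. BOP(t) = r × max(0, t − L), capped at 100% of sites. Lag L has mean 6 days and SD 2.5. Rate r has mean 2 points/day and log-SD 0.4.

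- Placebo, Day 21: 2 × (21 − 6) = 30
- 3-day delay, Day 21: 2 × (21 − 9) = 24
- 20% slower rise, Day 21: 1.6 × (21 − 6) = 24

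The same algebra gives about 16, 10 and 12.8 at Day 14. Day 7 needs simulation, because the lag straddles that visit.

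| Mean BOP (%) | Day 7 | Day 14 | Day 21 |
|---|---|---|---|
| Placebo | 3.1 | 16.0 | 30.0 |
| 3-day delay | 0.6 | 10.0 | 24.0 |
| 20% slower rise | 2.5 | 12.8 | 24.0 |

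Reading the single exam as Day 7 does not remove the problem. The delayed mean of 0.6 would also arise from a rise slowed by 1 − 0.6/3.1 = 81%.

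**Step 3. Several visits.** The placebo-minus-active gap at Days 7, 14 and 21 is 2.5, 6.0 and 6.0 for the delay (opens, then holds), and 0.6, 3.2 and 6.0 for the slower rise (keeps widening). Visit-wise differences by arm therefore carry onset information, and Section 8.0 states no analysis that uses it.

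**Step 4. Limit of means.** Suppose mean GI on placebo rises linearly to 1.0 at Day 21: 0, 0.333, 0.667, 1.0 on Days 0, 7, 14, 21. If everyone is one-third milder, multiplying by 2/3 gives 0, 0.222, 0.444, 0.667. If one third of participants have onset after Day 21 and the rest are unaffected, the means are 2/3 × placebo, the same four values. Only participant-level onset separates these two cases.

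**Step 5. Limit of a threshold.** In the Step 2 model, the share with BOP at 10% or more of sites is:

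| | By Day 14 | By Day 21 |
|---|---|---|
| Placebo | 75% | 99% |
| 3-day delay | 42% | 95% |
| 20% slower rise | 60% | 96% |

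Threshold onset falls by 75 − 60 = 15 percentage points at Day 14 with no delay at all, so it is not a pure measure of timing.

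**Step 6. Power for the 3-day delay.** Two-sided 5%, 30 per arm. The enrolment of 60 is from Section 4.2; equal allocation is assumed, because Section 6.1 names two groups without a ratio. Figures vary by one or two points between simulation runs.

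| Test | No noise | Baseline 0–8%, visit SD 3 | Baseline 0–8%, visit SD 5 |
|---|---|---|---|
| Day 7 means | 93% | – | – |
| Day 14 means | 86% | 78% | 68% |
| Day 21 means | 46% | – | – |
| Rank test on onset visit | 81% | 53% | 25% |

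With visit noise of SD 5 points, 14% of placebo participants already count as events at Day 0.

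**The case against.** Four arguments stand against the point.

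1. *An onset definition and a supporting time-to-event analysis are commonly left to an SAP.* That is fair, and the missing definition alone would not be a finding. What remains is that the protocol fixes clinical analyses and none of them answers the onset part of objective 3.
2. *The weekly scores already contain onset.* This stands. A reader might infer that onset is not measured at participant level. The documents do not support that, since GI and BOP are recorded at Days 0, 7, 14 and 21 and onset can be derived to within a week.
3. *Means over several visits can tell delay from milder disease.* This stands for a uniform shift (Step 3) and fails for the mixture in Step 4. The inability is exact for a single visit and should not be claimed for every comparison of means.
4. *A threshold analysis has its own weakness.* This stands. It also responds to slower progression, and reusing an entry cut-off as the event line places some eligible participants next to it. A reader might infer from 46% against 81% that onset analysis is more powerful, but that contrast comes from choosing Day 21. Day 7 and Day 14 means do at least as well, and with noise Day 14 means do better.

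**Conclusion.** The point holds in a limited form: onset is a stated objective and delaying it is an overview aim, but the clinical analyses fixed in Section 8.0 do not address it. At a single visit the ambiguity is complete: 24% against 30% at Day 21 under either mechanism. That figure rests on the assumed lag, growth rate and effect sizes. The logic does not, because any single lower mean can be matched by a suitably slower rise.

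A reader might also take delayed onset to be the trial's primary or headline claim. The documents do not say so: no objective is named primary, microbiome modulation and prevention come first, and the overview pairs delay with faster resolution.

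The consequence is for interpretation. As written, the trial could support reduced severity but not delayed onset.

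**What to change.** Use data already collected.

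- **(a) Visit-wise comparison.** Compare arms on GI and BOP at Days 0, 7, 14 and 21 in a repeated-measures model with arm, visit, arm-by-visit and baseline. Report the arm difference at each visit. Take baseline from Visit 1 (Day -14), since Day 0 follows two weeks of product.
- **(b) Participant-level onset.** Before unblinding, define onset as the first visit at which a stated share of sites is inflamed on a named index. Inclusion criterion 3 is a starting point, but it names no index. Allow for eligible participants who begin close to that line, for example by requiring a rise from Day 0. Compare onset visit between arms with a discrete-time or interval-censored model, and report the proportion affected by each visit.
- **(c) Stated limits.** Say that onset is known only to within 7 days, and that a shift in threshold onset can also reflect slower progression and must be read together with (a). If (a) and (b) are not added, limit the conclusion to reduced severity.

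Claim no power gain over visit-wise means. The cost is one definition and two analyses, with no extra visits or samples. The downsides are that the threshold must be fixed in advance and that dichotomising loses some precision.
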